5.8.a. Aim 1 Evaluation Plan. Data for Aim 1 will come from the VA Corporate Data Warehouse (CDW) and other VA databases, such as the VA COVID-19 Shared Data Resource. Outcome data will include receipt of a COVID-19 vaccination (one or more doses of Pfizer, Moderna, Johnson and Johnson, or other WHO-authorized vaccine; completed primary series with two doses of Pfizer, Moderna, one dose of Johnson and Johnson, or the specified number of doses for other WHO-authorized vaccines) and receipt of the seasonal flu vaccine (exploratory hypothesis) during the one-year trial. Covariates will include baseline demographics (e.g., age, race/ethnicity, gender, service connection), clinical and mental health diagnoses, and medications and healthcare utilization in the year prior to the start of the trial (e.g., VA and non-VA primary care visits, inpatient hospitalizations). The primary data sources for VA-administered vaccines are the ORDCOVID Vaccine tables, which are enhancements of the CDW Immunization table and is updated weekly. Immunizations performed outside VHA for which the administration fees are reimbursed by VHA will be ascertained from CDW Community Care data in the Payment Integrity Tool (PIT) files and the Integrated Veteran Care Consolidated Data Set. which replaced PIT. Immunizations for which administration fees are reimbursed by Medicare will be ascertained from the Centers for Medicare and Medicaid Services (CMS) Institutional Outpatient, Carrier, and Medicare Advantage files using the guarterly and annual updates as they become available through the VA Information Resource Center (VIREC). Aggregate data for county vaccination rates for adults older and younger than 65, by week, are available from the CDC COVID Data Tracker dataset "COVID-19 Vaccinations in the United States, by County". (See Data Analysis section below for plan to ascertain vaccination status for Veterans who receive COVID-19 vaccination outside of VA in which vaccination data is not accessible to VA researchers.)

5.8.b. Aim 2 Evaluation Plan. Data for Aim 2 will come from Veteran quantitative surveys and qualitative interviews. Data collection methods for Aim 2 will be telephone interview administered. We will use data from CDW to send opt-out letters to purposeful samples of newly vaccinated and unvaccinated Veterans. When telephone contact is made with potential subjects, we will introduce the study and conduct the initial telephone eligibility screen (See Appendix Draft Phone Eligibility Script/Screener.) We will ask the minimum number of required screening questions to gauge potential interest and study eligibility. Telephone eligibility screening questions will confirm interest in and ability to participate in a research study; vaccination status and participation in another COVID-19 research study. Study staff will determine if the potential participant is at a VAI or UC site. If the individual is interested in participating and study eligibility criteria are met, we will conduct informed consent (IC) using Docusign or mailed consents. During the IC process, we will ask the Veteran if they are willing to also participate in a separate qualitative interview.

The Veteran self-report survey developed for this study was informed by the Behavioral and Social Drivers of Vaccination (BeSD) World Health Organization model.³⁰ The W.H.O model was used to identify the predictors of COVID-19 vaccine acceptance in the development of the study survey (**see draft version of the Veteran survey**). The BeSD model includes four domains: What people Think and Feel, Social Processes, Motivation, and Practical Issues. The constructs within each domain are: Thinking and Feeling: COVID experience, perceived risk, vaccine confidence, mitigation behaviors, and COVID beliefs; Practical Factors: COVID impacts, competing demands, and health problems; Social Processes: trust, social norms, discrimination, and information sources; Motivation: intention, location, motivators, and barriers. Other domains included in the draft version of the Veteran survey include seasonal flu and other

vaccines (exploratory hypothesis), VA primary care experience, health status, and demographics.

The source for each question is annotated in the draft survey (see **Appendix**, **Draft Survey**). The following summarizes the sources for different parts of the Veteran survey. The survey items based on the BeSD model are from the CDC U.S. Vaccine Confidence Survey Question Bank, CDC COVID-19 Community Survey Question Bank, and VA QUERI Rapid Response Team COVID-19 SHEP Survey. The COVID impacts questions are from the NIH/VA/DoD Pain Management Collaboratory COVID Impacts survey. The competing demands questions are from the VA ACORN Survey. COVID-19 vaccine barriers guestion are from the NIH CEAL and SHEP surveys. The racial discrimination guestions are from the Williams Discrimination Scale that was adapted for Veterans by LRM Hausmann et al. The trusted sources of information guestions are from the Johns Hopkins COVID-19 Community Response Survey. The seasonal flu and other vaccine questions are from the San Francisco VAHCS Flu Vaccine Project and the Columbia University Collaborative Cohort of Cohorts for COVID-19 Research. The substance use questions include the 3-item AUDIT-C (Alcohol Use Disorders Identification Test) used by VHA as an alcohol use screener and PhenX Toolkit measures are used for cigarette smoking, vaping, and marijuana smoking status. The primary care experience questions are from the VA QUERI Rapid Response Team COVID-19 SHEP Survey.

Qualitative interviews will be conducted on a subset of Veterans who completed the quantitative survey according to the purposive sampling scheme described above. The qualitative interview will be audio-recorded. The audio consent will be included in the informed consent document Veterans will sign prior to completing the quantitative survey. If participants choose not to be audio-recorded, they may still participate in the quantitative survey. The consent document will have a check box in the qualitative interview section for "agree to be audio-recorded" or "do not agree to be audio-recorded." The qualitative interview will focus on a more detailed discussion about factors contributing to their decision to get or not to get the COVID-19 vaccine (see Appendix Draft Aim 2 Qualitative Interview Guides). We will also examine Veterans' interactions with VA HCPs and staff about COVID-19 vaccination to understand if and how the VAI impacted their vaccination decision. Other topics include previous/current barriers to getting the vaccine and ideas about how to get more Veterans vaccinated. We expect the qualitative interview will take 45-60 minutes to complete.

5.8.c. Aim 3 Evaluation Plan. The Aim 3 qualitative interviews with HCPs and staff will occur approximately 6- and 12-months after the trial start date for each site. The Aim 3 qualitative interviews will take place by phone. The interview guide questions will be organized around the i-PARiHS constructs of Innovation/Intervention, Recipient, Context, and Facilitation. Mid- and end-of-trial qualitative data will be collected by research assistants with qualitative data experience supervised by Drs. [name] and [name]. The general outline for the interview guides will include an open-ended grand tour prompt (e.g., "Tell me about your experience with the Vaccine Acceptance Intervention"). Follow-up probes will address barriers and facilitators and the i-PARiHS constructs: Innovation (e.g., what worked well/not so well), Recipient (e.g., how could we get more primary care staff and providers to participate in the Vaccine Acceptance Intervention (e.g., other community, VA, VAMC, and clinic efforts to increase vaccine acceptance), and Facilitation (e.g., how could the facilitation team efforts be more effective) (see Appendix, Draft VA Staff Interview Guides). We expect the HCP and staff verbal consent process and qualitative interviews will take approximately 1 hour (consent 15 minutes; interview 45 minutes) to complete.

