8.1 Privacy and Confidentiality

8.2 Veteran Participants. Our proposed research plan involves VA-enrolled Veterans receiving care in a VISN 16 or 21 primary care clinic. We will utilize VA CDW data and other VA administrative databases to examine COVID-19 and influenza vaccine acceptance and potential predictors of Veteran vaccine acceptance including sociodemographic characteristics, mental health and medical diagnoses, and other health services utilization variables among Veterans in enrolled clinics in VISN 16 and 21. We will conduct brief surveys and qualitative interviews with a purposive sample of Veterans from enrolled sites who both received and did not receive the COVID-19 vaccine. Protected health information, as described above will be collected and stored using processes described below. Study results will be reported only in aggregate. No participant names will be used in any reports or publications.

8.2.a VA administrative data. VA CDW and other VA administrative data will be accessed through the VA Informatics and Computing Infrastructure (VINCI), an initiative to improve researchers' access to VA data and to facilitate the analysis of those data while ensuring Veterans' privacy and data security. Domains in CDW that will be accessed include Veteran sociodemographics, ICN (Integration Control Number), health services utilization, associated ICD-10 diagnoses, COVID-19 vaccine acceptance, current and prior year influenza vaccine acceptance.

8.2.b Veteran Qualitative Interviews. Qualitative interviews will be conducted by study personnel by phone. Research personnel will work in a private location. Verbal consent will be obtained over the phone and documented in study records prior to starting the interview audio-recording and the participant will not be named after that. If a participant's name is inadvertently recorded, it will be electronically stripped from the recording. Audio recordings will be retained in accordance with the VHA Records Control Schedule.

8.3Stakeholder Participants. Mid-trial and end-of-trial qualitative interviews will be conducted with VISN 16 and 21 staff with the goal of learning which aspects of the intervention and implementation were helpful, or not helpful, in improving Veteran COVID-19 vaccine acceptance. Stakeholders will be asked to consent verbally to participation. All qualitative interviews will be conducted by phone.

8.4 Data Security.

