5.1.3 Exploratory Outcomes

Flu vaccination: Receipt of seasonal flu vaccination in all Veterans with one or more primary care visit(s) at a participating VA facility within the past year.

COVID-19 First Booster: Receipt of first COVID-19 booster by those eligible for the booster within 3 months prior to the end of the study period. This includes Veterans who were eligible and had one or more primary care visit(s) at a participating VA facility within the year prior to study period, but unboosted at the start of the trial, as well as those who completed their primary series during the trial and became eligible for the booster.

5.2 Aim 2

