8. DATA COLLECTION AND DATA FREEZE

8.1 Aim 1

Data from Aim 1 will be obtained from the VA Corporate Data Warehouse (CDW) and supplemented with data from other VA administrative data (e.g., VA COVID-19 Shared Data Resource, Medicare data). Table 2 provides the study initiation for each site and the last day of 12-month follow-up for eligible participants. In the subsequent Project Modification, we added two additional follow-up timepoints of 15 and 18 months after study site initiation. The last follow-up for any participant will be 10/19/2023 – at which point the trial database will be closed/frozen and be considered ready for final analysis.

Table 2: Study initiation and follow-up completion by study site

Study Site	Initiation Date	Follow-up	
		Completion Date	
Little Rock, AR	02/14/2022	02/13/2023	
Fayetteville, AR	02/14/2022	02/13/2023	
Las Vegas, NV	03/08/2022	03/07/2023	
Reno, NV	03/08/2022	03/07/2023	
Palo Alto, CA	03/21/2022	03/20/2023	
Northern CA, CA	03/21/2022	03/20/2023	
Honolulu, HI	03/23/2022	03/22/2023	
Fresno, CA	03/23/2022	03/22/2023	
New Orleans, LA	04/20/2022	04/19/2023	
Houston, TX	04/20/2022	04/19/2023	

8.2 Aim 2

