9.1.6 Analysis of Exploratory Outcomes

No control for multiplicity will be performed for exploratory outcomes. We will use the same methods proposed to analyze the primary and secondary outcomes to analyze receipt of a booster vaccination and flu vaccination. We will adapt methods presented by Sinclair et al. (2012) to estimate the spill-over effect of the intervention by analyzing receipt of seasonal flu vaccination. CDC guidelines on the minimum length of time between COVID-19 primary series completion and booster eligibility decreased during the study period. We will use the most recent guideline in effect during our study period, which was a minimum of 60 days from primary series completion to receipt of the first booster. In instances where a third mRNA vaccine dose was administered prior to 60-days following the second mRNA dose, that is classified as an additional primary series dose per CDC guidelines for Veterans with immunosuppression, and the date of that vaccination is defined as the date of primary series completion. Due to difficulties ascertaining which Veterans have immunosuppression, and the relatively loose guidelines for which conditions qualify, third doses have been defined empirically based on vaccination dates.

Because of evolving guidance on COVID vaccinations (products, dosing, etc.) in the context of fluctuating background COVID-19 prevalence at different VAHCS sites combined with seasonal flu vaccination in the Fall and Winter months, we expect temporal and site trends. Therefore, we plan to conduct the following exploratory analyses: (1) adjust for time-dependent variables; and (2) perform analyses stratified by time period and site.

9.2 Aim 2

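### The exploratory flu outcome names no flu season and its model omits prior-season flu vaccination, which costs clarity and precision but does not by itself bias the comparison

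*Protocol*

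**What the plan says.** **Outcome.** Protocol 5.8.a counts "receipt of the seasonal flu vaccine (exploratory hypothesis) during the one-year trial". SAP 5.1.3 defines it as "Receipt of seasonal flu vaccination in all Veterans with one or more primary care visit(s) at a participating VA facility within the past year". Neither gives a season, a first date or a last date. The booster outcome, next in the same SAP section, does have an eligibility rule tied to the end of the study period.

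**Window.** SAP 8.1 states that "Table 2 provides the study initiation for each site and the last day of 12-month follow-up for eligible participants". The sites start on five different dates. The same section reports that "we added two additional follow-up timepoints of 15 and 18 months after study site initiation" and does not say whether flu is analysed at those timepoints.

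**Timing of flu vaccination.** The only indication is in SAP 9.1.6 and the matching text in Protocol 5.9, which expect temporal and site trends "combined with seasonal flu vaccination in the Fall and Winter months".

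**Model.** SAP 9.1.6 says "We will use the same methods proposed to analyze the primary and secondary outcomes to analyze receipt of a booster vaccination and flu vaccination". SAP 9.1.1 applies adjustment for VISN and baseline vaccination rate to every analysis, and SAP 9.1.4 adds age, race/ethnicity, gender and prior-year utilization. The protocol's Randomization section identifies the baseline rate as that of the COVID-19 primary series.

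**Data.** Protocol 8.2.a includes "current and prior year influenza vaccine acceptance" among the warehouse domains to be accessed.

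**The concern.** Flu vaccine is given by season, but the outcome is counted by trial year. A dose given on 20 February 2022 would count at Little Rock, where follow-up had begun six days before, and would not count at Houston, which started on 20 April. A late 2021-22 dose can therefore register as a response to an intervention that had only just begun, even if the Veteran later declines the 2022-23 vaccine. The sites also close at different points of winter and spring 2023.

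The flu model adjusts for a COVID-19 rate and not for earlier flu vaccination. A Veteran's prior-season flu status is the baseline value of this outcome and can be expected to predict it well. With five sites per arm, chance differences in habitual flu uptake are a real possibility, and the planned covariates address them only indirectly.

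At stake are the interpretation and precision of the spill-over result.

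**Working it through.** **1. Table 2 windows.** Counting both end dates, each of the ten windows is 365 days, so the table is consistent. Starts run from 14 February to 20 April 2022 and ends from 13 February to 19 April 2023, a spread of 65 days at both ends.

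**2. Reach into 2021-22.** The documents give no season end date, so several are assumed. Tail days = max(0, assumed end − site start + 1).

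| Site start (2022) | End 28 Feb | End 20 Mar | End 31 Mar | End 30 Apr |
|---|---|---|---|---|
| 14 Feb: Little Rock, Fayetteville | 15 | 35 | 46 | 76 |
| 8 Mar: Las Vegas, Reno | 0 | 13 | 24 | 54 |
| 21 Mar: Palo Alto, Northern CA | 0 | 0 | 11 | 41 |
| 23 Mar: Honolulu, Fresno | 0 | 0 | 9 | 39 |
| 20 Apr: New Orleans, Houston | 0 | 0 | 0 | 11 |
| Windows reached | 2 of 10 | 4 of 10 | 8 of 10 | 10 of 10 |

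If winter ends on 28 February or 20 March, 2 to 4 windows touch the earlier season. All ten do only if the season is taken to run into late April.

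**3. Coverage of 2022-23.** Every window contains all 91 days from 1 September to 30 November 2022. Of the 181 days from 1 September 2022 to 28 February 2023, the two earliest sites cover 166 and the other eight cover all 181.

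**4. Common period.** The latest start is 20 April 2022 and the earliest end is 13 February 2023, so 300 days are shared by all sites. The period 1 August 2022 to 13 February 2023 (31+30+31+30+31+31+13 = 197 days) lies inside every window.

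**5. Covariates against available data.** Planned: VISN, COVID-19 baseline rate, age, race/ethnicity, gender, utilization. Listed for access but not in the model: prior-year influenza vaccination.

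**6. What the missing covariate could be worth.** No power is stated for flu, so this is only an illustration using the plan's own design. With M = 1000 Veterans per clinic, K clinics per VAHCS and 5 VAHCS per arm:

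- Design effect DE = 1 + (M − 1)(0.07) + M(K − 1)(0.02). For K = 9: 1 + 69.93 + 160 = 230.93.
- The detectable difference d solves d = (z₀.₉₇₅ + z₀.₉₀)·√{[p(1−p) + q(1−q)]·DE·(1−r²)/(5KM)}, with q = p + d and r the correlation with the added baseline.

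With r = 0 this gives 9.64, 9.51, 11.86, 11.71, 13.35, 13.19, 14.42 and 14.25 points, against 9.7, 9.6, 12.0, 11.8, 13.5, 13.3, 14.6 and 14.4 in SAP Table 1. All are within 1.3% in relative terms, so the formula reproduces the plan.

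For flu, assume a usual-care rate of 40% to 50%, the same ICCs and K = 9 (neither the rate nor r is in the documents):

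| r | p = 40% | p = 50% |
|---|---|---|
| 0 | 16.2 | 16.0 |
| 0.5 | 14.1 | 13.9 |
| 0.7 | 11.6 | 11.6 |
| 0.9 | 7.1 | 7.1 |

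This is an upper-end picture. It shrinks the whole clustered variance by 1 − r², while the planned covariates already explain some of it. Most of DE comes from clinics and VAHCS, so a Veteran-level covariate helps mainly as far as those clusters differ in prior flu uptake.

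**The case against.** **Equal exposure.** The current rule gives every site the same 12 months from initiation, a legitimate choice for a trial-period outcome. This stands as a reason to keep that count as a sensitivity analysis.

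**The plan anticipates seasonality.** SAP 9.1.6 announces exploratory adjustment for time-dependent variables and strata by period and site, and SAP 9.1.2 provides sensitivity adjustment for characteristics that look imbalanced. Both are relevant. Neither names a flu season or prior flu status, so the gap narrows but stays open.

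**Bias between arms.** A reader might infer that the offset start dates favour one arm. The documents do not support this. Sites start in five same-date pairs, each within one VISN. If each pair holds one site per arm, the offset balances, but the arm of each site is not stated.

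**Season mixing.** A reader might also infer that the outcome fails to measure one season's uptake. Steps 2 and 3 show that this goes too far.

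**Omitted baseline.** Leaving out a prognostic covariate does not by itself bias a randomised comparison. This stands, and it limits the point to precision and chance imbalance.

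**Later timepoints.** At 18 months the latest sites would reach 19 October 2023, in another fall. But Protocol 5.8.a limits flu to the one-year trial and the model carried over is a 12-month model, so this matters only if flu is analysed later.

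**Conclusion.** The point holds in a limited form. The flu outcome measures mainly 2022-23 uptake plus a tail of late 2021-22 doses that depends on the site and on where the season is taken to end. The share of doses in the tail is not in the documents. It is probably small, because flu vaccination is placed in fall and winter and every window holds the whole of fall 2022. No difference between arms is shown.

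The more useful part concerns the model. Prior-season flu status is absent although the protocol plans access to it. With ten sites, the cost is lost precision and unadjusted chance imbalance. The figures in step 6 rest on assumed rates and correlations and show direction only.

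The outcome is exploratory, with no power claim and no multiplicity control. Primary and secondary results are untouched, and the priority is low.

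**What to change.** 1. **SAP 9.1.6.** Keep VISN and the COVID-19 baseline rate in the flu model. Randomization was constrained on that rate and SAP 9.1.1 requires adjustment for it in all analyses, so it should not be swapped for a flu rate. Add each Veteran's own 2021-22 flu vaccination status, recorded before 14 February 2022, the first initiation date. A Veteran-level covariate uses no site-level degrees of freedom.
2. **SAP 5.1.3.** Count at least one 2022-23 seasonal dose in one calendar window inside every site's follow-up, for example 1 August 2022 to 13 February 2023. The August start is an assumption for the study team to settle. Report the site-specific 12-month count as a sensitivity analysis.
3. **SAP 8.1.** State whether the 15- and 18-month timepoints apply to flu.

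**Cost.** SAP wording, a date filter and one covariate. The protocol says the prior-year data will be accessed. It does not say that they have been extracted or that prior year means 2021-22, so both need confirming. A few doses after 13 February 2023 at the eight later-closing sites would drop out of the main count. Time since initiation at the common closing date would run from 300 to 365 days, a difference of up to 65 days between sites. SAP section 9 permits changes only up to final data lock and before unblinding; if that point has passed, label the revised analysis post hoc.

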5.9 Data Analysis

The data analysis team consists of [name] (Associate Professor of Biostatistics, Yale University and VA Connecticut Health Care System, WOC), who is experienced in conducting data analyses for multi-site randomized clinical trials in and outside

of the VA healthcare system. She currently serves as the lead biostatistician on our NIH-funded wHOPE trial and prepares the open DSMB reports for this multi-site VA trial of pain management approaches for Veterans with chronic pain. [name] will work closely with [name], biostatistician, and [name], our data analyst based at the SFVAHCS, who has well over a decade's experience conducting analyses using VA EHR data and specially has experience in accessing non-VA community care data and the COVID Shared Data Resource. Both [name], [name], and [name] will be supported by our experienced data manager, [name], who built and now oversees the database application for the wHOPE trial and has a similar data application planned for this trial. [name] will oversee the preparation of the open DSMB reports but will not prepare any closed DSMB reports or see any data by treatment arm. [name] and [name] will prepare the closed DSMB reports. In addition, we will develop a detailed statistical analysis plan a priori to guard against bias should [name] inadvertently become unblinded. The details of our data analysis plan by study aim are as follows:

Specific Aim 1 Conduct a one-year pragmatic cluster randomized controlled trial of a COVID-19 Vaccine Acceptance Intervention (VAI) to determine whether, compared to Usual Care sites, Intervention sites achieve:

- *o H1a:* A greater proportion of Veterans that receives *one or more doses* of COVID-19 vaccination, whether as a primary series or booster (*primary outcome*)
- *H1b:* A greater proportion of previously unvaccinated Veterans that completes COVID-19 vaccination primary series.
 Exploratory hypothesis H1c: A greater proportion of Veterans that receives at least one COVID booster; a greater proportion of Veterans completes seasonal flu vaccination.

In addition, we will utilize the VA Corporate Data Warehouse (CDW) and other VA administrative data (e.g., VA Shared COVID-19 Data Resource), to assess other independent predictors of vaccine acceptance, including sociodemographic factors, clinical diagnoses, and health services utilization.

Sample Size Determination: Of the 16 VAHCS in VHA region 16 and 21, 10 VAHCS agreed to participate in the study, with an average of 9 to 10 clinics per VAHCS, and an average of at least 1,000 Veterans per clinic. These numbers were based on conservative projections of the number of Veterans at the time of randomization and account for missing vaccination (i.e., misclassification) status for Veterans who may have been vaccinated outside of the VA. We hypothesize that the larger proportion of Veterans will get vaccinated (both first and fully) within 12 months in the VAI arm compared to usual care. Calculations were conducted with PASS 19 (Kaysville, Utah) using sample size for mixed models for two sample proportions with a 3-level hierarchical design assuming an intra-cluster correlation (ICC) of 0.07 for individuals within a clinic and an ICC of 0.02 for clinics within a VAHCS.¹¹⁴ With a type I error rate of 0.05 (two-sided) we will have at least 90% power to detect between a 9.6% and 14.6% difference in vaccination rates assuming a rate in the usual care group ranging from 5% to 20% and a total sample size of 90,000 to 100,000. **Table 4** shows details of different scenarios.

Table 4: Detectable difference for comparing 2 proportions in a hierarchical model assuming 5 VAHCS per arm with on average 9-10 clinics per VAHCS and, on average, 1000 individuals per CBOC/clinic, 90% power, type I error of 5% (two-sided) and level ICC of 0.07 and level 2 ICC of 0.02

| Total Sample Size | Clinics VAMC* | Rate in Usual Care | Detectable difference |
|-------------------|---------------|-----------------------|--------------------------|
| 90,000 | 9 | 5% | 9.7% |

| 100,000 | 10 | 5% | 9.6% |
|---------|----|-----|-------|
| 90,000 | 9 | 10% | 12.0% |
| 100,000 | 10 | 10% | 11.8% |
| 90,000 | 9 | 15% | 13.5% |
| 100,000 | 10 | 15% | 13.3% |
| 90,000 | 9 | 20% | 14.6% |
| 100,000 | 10 | 20% | 14.4% |

*Only presented 9 and 10 clinics per VAMC for baseline rate of 5%- a negligible difference in the detectable difference between 9 and 10.

These calculations are for both the primary outcome (any dose) and secondary outcome (primary vaccination series completion). Since there is only one secondary outcome, no multiple testing procedures will be applied, and a type I error rate of 5% will also be used for this outcome.

Analytic Plan: All analyses will be performed using SAS v9.4 (Cary, NC) or the latest version of R (https://cran.r-project.org/). Statistical tests and confidence intervals will be two-sided and carried out at the 5% level of statistical significance. All analyses will follow the intention to treat principle, that is, any previously Veteran at the start of the trial who receives VA inpatient or outpatient clinic services at a participating VAMC will be considered in the denominator of the vaccination rate regardless of whether they received the intervention. Since randomization will be stratified by VISN and at the level of VAMC, but analysis will be conducted at the individual level, we will implement covariate constrained randomization for key variables (e.g., primary series vaccination rates, rural/urban distribution and facility size) and assess the adequacy of the randomization by comparing baseline characteristics between the two treatment groups.¹¹⁵ No statistical tests will be used to assess these comparisons. Variables will be summarized using descriptive statistics (means, proportions, etc.) and plots (e.g., box and whisker). Variables that appear to be different between the VAI and Usual Care sites will be adjusted for in sensitivity analyses. For analysis of the primary (one or more doses from a primary series or booster) and secondary outcome (primary series completion), we will use a multi-level model that takes into account the hierarchical clustering¹¹⁶ and adjusts for variables included in the covariate constrained randomization (e.g., rural/urban distribution and facility size) to estimate the difference in proportion of vaccinated Veterans at 12 months between VAI and Usual Care. We will adapt methods presented by Sinclair et al.¹¹⁷ to estimate the spill-over effect of the intervention (i.e., impact on the receipt of seasonal flu vaccination).

The uncertainty in vaccine records ascertainment is pertinent to discuss prior to describing how we will analyze the primary, secondary, and exploratory outcomes with standard and sensitivity analyses. There will be Veterans who receive their COVID-19 vaccinations outside of the VA system or from venues not currently captured in VA databases (i.e., State fairs, shopping malls etc.). This could inflate our denominator of unvaccinated Veterans at the start of the trial (i.e., false negatives – Veterans are actually vaccinated). It could also decrease our numerator during the trial because we could miss Veterans who received COVID-19 vaccines during the study follow-up period at non-VA sites not captured in VA data. There are two main avenues to supplement missing vaccine information in VA records; however, both have important limitations.

First, we will supplement VA vaccination records with Medicare claims data. While the federal government paid for the vaccine product, providers were permitted to bill for the cost of administering the vaccines. Based on analyses from the VA Information Resource Center (VIReC) in 2021, linking Medicare data substantially improved ascertainment. There are a few limitations. First, due to a lag, claims data will not be available for the complete study period. For Veterans enrolled in traditional Medicare fee-for-service, which account for approximately 70% of Medicare-enrolled Veterans, we anticipate data being available through 2022.¹²⁹ For Veterans enrolled in Medicare Advantage (i.e., managed care programs), data will only be

available through 2021. Second, during the early phases of vaccine rollout in 2021 when mass vaccination clinics had been common, Centers for Medicare and Medicaid Services estimated that claims were never submitted for as many as half of Medicare-age people.

Second, VHA has been developing a health information exchange with state Immunization Information Systems (IIS) in partnership with CDC to query and report Veteran immunization records. This exchange, known as the IZ Gateway, began querying state registries for 9 of the 10 study sites during July and August of 2023. Unfortunately, VHA does not plan to query state registries retrospectively for all Veterans. Instead, VHA will query individual Veterans' records when they receive VA health services. Accordingly, we anticipate differential vaccine ascertainment in which Veterans who receive care from the time the Gateway was activated in their home state until the final data lock for this study will have near-complete vaccine ascertainment; in contrast, Veterans who do not receive care during this period will have lesscomplete ascertainment. Vaccine records populated through the Gateway can be identified which will help us to evaluate potential biases resulting from the timing of the Gateway rollout. For the main analyses, records populated through the IZ Gateway are being removed from the analytic dataset to avoid differential bias.

Due to limitations of the IZ Gateway and Medicare data, we will utilize one or more of several methods to ascertain the missing vaccination records and its impact on our estimates. These include comparison of our rates to those published by state and federal authorities for our VISNs or comparison of our rates to those reported by national and local VA dashboards. Alternatively, to estimate population levels of underreporting, we may need to utilize survey sampling methodology and probability weighting to randomly survey Veterans with no documentation of COVID vaccination. In sum, primary analyses for Aim 1 will utilize only VA electronic health data to ascertain Veterans' vaccination status. We will also conduct sensitivity analyses that incorporate all available data sources (e.g., electronic health records; Medicare; state-level records; IZ Gateway).

Sensitivity Analyses

Expanding Analyses to Include Vaccination Records from Medicare/Medicaid and IZ Gateway

We plan to incorporate the vaccination records from Medicare/Medicaid and the IZ gateway and run sensitivity analyses for the primary outcome. These supportive analyses will provide variation in the estimated intervention effect related to incorporating external sources of vaccination records. On account of the IZ Gateway querying state IIS records on a prospective basis, these sensitivity analyses will focus on Veterans who have received care since the IZ Gateway was activated in their home states, which for the study sites happened during July or August of 2023. The specified statistical model is identical to that laid out in the analytic plan.

Missing Outcomes/Misclassification of Vaccination Status

We will conduct sensitivity analyses with a Bayesian form of multi-level logistic regression that uses the same core hierarchical model.¹³⁰ Bayesian methods estimate parameter values (e.g., odds ratio of vaccine uptake between intervention arms) by summarizing sequentially drawn values from probability distributions with parameters updated jointly by the observed data (vaccination counts, clinic, and VAMC characteristics, etc.) and updated values of other model parameters. For our needs, the Bayesian logistic regression will incorporate a multiple imputation step that corrects the observed vaccination rates in two different ways. We can correct the total number of eligible Veterans, i.e., the denominator at each facility due to misclassifying them as unvaccinated prior to study start. Second, we can correct the count of

observed vaccinations over the course of the study at each study site, i.e., the numerator, due to imperfect vaccination records ascertainment.

For the primary aim, we assume no uncertainty in Veteran eligibility since we will be using all Veterans with at least one primary care visit. This entails not subtracting a modeled probabilistic number of Veterans from the denominator of the rate of vaccination per facility, whereas the multiple imputation adds a random quantity to the count of instances of any vaccine dose (i.e., the numerator) to represent the unknown vaccinations over the course of the study that, if ignored, would be labeled as unvaccinated in the eligible sample.

Each clinic's corrected quantity will be equal to a probabilistically modeled rate of misclassified vaccinations multiplied by the count of those Veterans labeled as unvaccinated according to the available data. The distribution for each timepoint's rate of misclassified vaccinations will be assumed to follow a truncated Beta distribution with a lower bound estimated from available Medicare data from 2021-2022, upper bound, mode (most likely value), lower and upper percentile values determined by investigators. The Bayesian framework then updates the model's parameters with these corrected vaccination counts instead of the observed vaccination counts. We will assess changes in the parameter estimates across a range of assumptions for the two misclassification rates and summarize the results with posterior probabilities of a non-null intervention effect, 95% credible intervals, and posterior means and medians.

Analysis of Secondary Outcome

We will use the same hierarchical, multi-level method for binary outcomes to analyze the secondary outcome of primary series completion in Veterans reported to not have initiated or completed the COVID-19 primary series at randomization. The model structure and adjustments are identical to that for the primary outcome. No multiple testing will be considered since there is only one secondary outcome. We will report the difference in rates between the VAI and usual care arms and the 95% confidence interval.

Sensitivity Analyses

Expanding Analyses to Vaccination Records from Medicare/Medicaid and IZ Gateway

We plan to incorporate the vaccination records from Medicare/Medicaid and the IZ gateway and run sensitivity analyses for the secondary outcome. The motivation and analysis model are identical to that laid out above. We will include Veteran records provided by these additional data sources who were not reported to have completed or initiated the primary series at randomization.

Missing Outcomes/Misclassification of Vaccination Status

